9.2 STATISTICAL ANALYSES

9.2.1 General considerations

The baseline value is defined as the last available value before the first dose of double-blind IMP. For participants randomized but not treated, the baseline value is defined as the last available value before randomization.

For endpoints defined using the data collected on the eDiary (such as NCS and TSS), baseline is defined as the average of the scores in the 7 days prior to randomization; for the baseline to EOT analysis, the average of the scores from the preceding 28 days to the corresponding timepoint will be defined as the analysis score for that timepoint.

Unless otherwise specified, analyses will be performed by intervention group (and overall for baseline and demographics characteristics).

The observation period will be divided into 4 segments:

- The **pre-treatment** period is defined as the period up to first IMP administration.
- The **TE period** is defined as the period from the first IMP administration to the last IMP administration + 154 days (ie, to the end of 20-week safety follow-up period).
The TE period includes the following 2 periods:
 - The **on-treatment period** defined as the period from the first IMP administration to the last administration of the IMP + 14 days.
 - The **residual treatment period** defined as the period from the end of the on-treatment period to the end of the TE period.
- The **post-treatment period** defined as the period from the end of the TE period.

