EFC18418 is a Phase 3 multinational randomized, double-blind, placebo-controlled trial with 3 parallel groups aimed at evaluating the efficacy, safety, and tolerability of 2 different dosing regimens of itepekimab in participants diagnosed with CRSwNP. During the study, participants will receive MFNS as INCS. In Japan, participants on INCS (MFNS or other INCS) will continue taking their daily INCS with a stable dose through all periods of the study. In Japan, participants not on INCS prior to screening, will receive MFNS during screening and throughout the study. In China, participants will continue their stable daily dose of INCS (which may include MFNS or other INCS) during the screening period and throughout the study. The study interventions consist of SC administration of itepekimab at a dose of 300 mg Q2W, itepekimab at a dose of 300 mg Q4W, or a matching placebo. A total of approximately 210 participants will be randomized in 1:1:1 fashion, and the intervention duration will be 52 weeks. Following the intervention period, an optional long term extension study may be available for participants in this study. Participants who are eligible and willing to participate in this study will directly roll over without a 20-week follow up period. For other participants (and in case the long- term extension study is not started or approved), participants will have a 20-week follow up period. It is estimated that approximately 95 sites may participate in this study.

Brief summary:

EFC18418 is a multinational, randomized, double-blind, placebo-controlled, parallel-group, Phase 3 study with 3 treatment groups. The purpose of the study is to evaluate the efficacy, safety and tolerability of 2 dosing regimens of itepekimab compared to placebo as add-on therapy to INCS in male and female participants with CRSwNP aged 18 years of age and older.

Study details include:

- The study duration (4-week screening, 52-week treatment, 20-week safety follow-up) will be up to 76 weeks. For participants transitioning to the LTS18420 study, the study duration will be 56 weeks.
- The treatment duration will be up to 52 weeks.
- The number of visits will be 9 site visits and 20 phone/home visits.

Number of participants:

Approximately 210 participants will be randomized.

Study arms and duration:

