Participants who satisfy the inclusion criteria will be randomized (1:1:1) to one of the following IMP intervention group to be administered for the planned 52-week intervention duration:

- Itepekimab 300 mg, administered as a single SC injection Q2W.
- Itepekimab 300 mg, administered as a single SC injection Q4W with alternating SC injection of matching placebo at the 2-week interval between active IMP.
- Placebo, administered as a single SC injection of matching placebo to itepekimab Q2W.

Randomization will be stratified by asthma/AERD status (no asthma, asthma only, asthma & AERD), and region (Asia or rest of the world) (Appendix 14 [Section 10.14](#) for AERD diagnosis).

Study intervention(s)

Investigational medicinal product(s)

Sterile itepekimab or matching placebo will be provided in PFS for SC administration. Each PFS contains a deliverable volume of 2 mL with an itepekimab concentration of 150 mg/mL or 0 mg/mL.

- Formulation: 2 mL solution for injections (150 mg/mL).
- Route(s) of administration: SC.
- Dose regimen: all participants will receive Q2W dosing to maintain the blind. Participants on Q4W will receive alternating doses of IMP and placebo.

AxMP

Mometasone nasal spray

- Formulation: Mometasone (50 µg/actuation) metered-dose nasal spray.
- Route(s) of administration: intranasal.
- Dose regimen: 2 actuations per nostril twice a day (total daily dose of 400 µg), starting at Visit 1, unless they are unable to tolerate or there is a specific regulatory requirement preventing use of this dose in which case they can stay on a lower dose regimen (200 µg) of MFNS.

Devices

The itepekimab PFS is classified as a combination product with an integral medical device where the principal mechanism of action is that of itepekimab. Medical devices for diagnostic interventions (eg, ECG) are not considered as 'investigational devices' in the context of this study.

Post-trial access to study medication

After the end of the study, a separate long-term study (LTS18420) may be offered to participants who completed the study and are still taking the IMP. This long-term study will allow to assess long-term safety and efficacy of the itepekimab and will be described in a separate protocol.

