
- a The screening period is 28 days +/- 7 days in duration to run in any participant on MFNS, and to collect baseline data. In Japan, participants on INCS (MFNS or other INCS) will continue taking their daily INCS with a stable dose through all periods of the study. In Japan, participants not on INCS prior to screening, will receive MFNS during screening and throughout the study. China participants should be on daily treatment with INCS prior to screening and will continue their daily INCS with a stable dose as background treatment during the screening and throughout the study. Participants receiving rescue medication with SCS or/and surgery during this period will not be randomized. Randomization Visit is defined as Day 1. All subsequent visits will be calculated using this as a reference. Window for subsequent visits is +/-3 days. Assessments/procedures at a site visit are performed in the following order if applicable: PROs and other questionnaires; procedures; safety and laboratory assessments; IMP administration.
- b Participants who prematurely discontinue from the study prior to completing the planned treatment period (ie, ETD), will attend the ETD visit and follow the assessments for EOT as shown in this table, and will be requested to attend the remaining follow up visits per the protocol schedule with a +/- 5-day window until the EOS.
- c Follow-up period is not applicable for those participants entering a LTS18420 if a LTS18420 for itepekimab is initiated and approved by Health Authorities and country and/or local IRB/IEC. In the absence of a LTS18420 all participants enter the follow-up period.

- d* Home visits/phone calls will be conducted at the following timepoints: Week 6 (Visit 5), Week 8 (Visit 6), Week 10 (Visit 7), Week 14 (Visit 9), Week 16 (Visit 10), Week 18 (Visit 11), Week 20 (Visit 12), Week 22 (Visit 13), Week 26 (Visit 15), Week 28 (Visit 16), Week 30 (Visit 17), Week 32 (Visit 18), Week 34 (Visit 19), Week 38 (Visit 21), Week 40 (Visit 22), Week 42 (Visit 23), Week 44 (Visit 24), Week 46 (Visit 25), Week 48 (Visit 26), Week 50 (Visit 27).
- e* Window of +/-3 days applies to all visits during IMP administration. Follow up/EOS has a +/-7 day window.
- f* Separate consent to be obtained for optional procedures (whole blood DNA, and serum/plasma sampling for archival; nasal brushing for RNA and cytology, blood for genomic variant analyses), and potentially for HIV test, if specific consent is locally required.

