- k* IMP (itepekimab or placebo) to be administered Q2W at the site. Participants should be monitored by site personnel for at least 30 minutes after administration of the first 3 IMP injections. Monitoring period may be extended as per country-specific requirements. Starting after Visit 4 (Week 4), IMP will be administered by the participant, caregiver, or healthcare professional at the participant's home or in a healthcare facility, depending on what is chosen, according to treatment allocation. If the participant or Investigator decides not to administer IMP at home, the IMP injections can be performed at the site. The last dose will be given 2 weeks prior to the planned EOT visit (Week 50).
- l* A CT scan should be performed at the Randomization Visit (up to 7 days before first administration of IMP), at Visit 14 (Week 24) +/- 7 days, and central reading will be used for comparison of baseline to Week 24. In countries for which a specific approval procedure for the CT scan is required by a different committee than the IEC/IRB, these countries will be exempted from all the planned study CT scans until approval from these committees is received. It is recommended to avoid the use of SCS as rescue therapy during Week 20 to Week 24. If a participant must use SCS during this period to control CRSwNP worsening/acute sinusitis based on Investigator judgment, the site should make every effort to schedule the Week 24 CT scan prior to SCS rescue therapy.
- m* An eDiary (ie, CRSwNP sinonasal symptom diary) is used for daily recording of nasal symptoms (from Visit 1 to EOS): 1) nasal congestion/obstruction, 2) anterior rhinorrhea (runny nose), 3) posterior rhinorrhea (post-nasal drip), 4) loss of sense of smell, 5) facial pain/pressure, and 6) headache. This device is dispensed at Visit 1, and information is downloaded from this device on the other indicated days. For endpoints defined using the data collected on the eDiary (such as NCS and TSS), baseline is defined as the average of the scores in the 7 days prior to randomization. Completion of a minimum of 4 out of 7 days is required prior to randomization.

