9.2.6.1 Adverse events

General common rules for adverse events

The AEs will be analyzed in the following 3 categories:

- Pre-treatment AEs: AEs that developed, worsened or became serious during the pre-treatment period.
- TEAEs: AEs that developed, worsened or became serious during the treatment-emergent period.
- Post-treatment AEs: AEs that developed, worsened or became serious during the post-treatment period.

Similarly, the deaths will be analyzed in the pre-treatment, TE and post-treatment periods.

Analysis of all adverse events

Adverse event incidence table will be provided by treatment group for all types of TEAEs: all TEAEs, all treatment emergent AESI (defined with a preferred term [PT] or a prespecified grouping), all treatment-emergent SAEs and all TEAEs leading to permanent treatment discontinuation.

The AE summaries will be generated with number (%) of participants experiencing at least 1 event.

Deaths will also be analyzed.

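### The treatment-emergent window runs past the end of observation for LTS18420 rollovers, so crude TEAE percentages pool unequal ascertainment windows

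*Protocol*

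**What the plan says.** Protocol Section 9.2.1 sets the TE period as the "period from the first IMP administration to the last IMP administration + 154 days (ie, to the end of 20-week safety follow-up period", with no exception for participants who enter the extension. Within it, the on-treatment period is "defined as the period from the first IMP administration to the last administration of the IMP + 14 days". The remainder is the residual treatment period.

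On the extension, Section 1.3 (footnote c) states: "Follow-up period is not applicable for those participants entering a LTS18420". The synopsis agrees ("Participants who are eligible and willing to participate in this study will directly roll over without a 20-week follow up period") and adds: "For participants transitioning to the LTS18420 study, the study duration will be 56 weeks". Section 4.4 makes EOT the last visit in this study for these participants. Without LTS18420, everyone enters follow-up.

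Rollover is restricted: the extension "may be offered to participants who completed the study and are still taking the IMP". The synopsis adds eligibility and willingness.

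Section 9.2.6.1 defines TEAEs over the whole TE period and gives the summary measure: "The AE summaries will be generated with number (%) of participants experiencing at least 1 event". Incidence of TEAEs, TESAEs and TEAESIs is a secondary endpoint, under an objective that compares itepekimab with placebo (Table 2).

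**The concern.** The TE definition treats last dose + 154 days and the end of the 20-week follow-up as the same date. For a rollover participant there is no follow-up, so most of the residual period is never observed in this study. A crude percentage counts that participant in the denominator as though the whole window had been seen.

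Who rolls over is decided after randomization. A participant who has surgery is permanently taken off IMP (Section 6.9.1), and one who meets a permanent-discontinuation rule in Section 7.1.1 is no longer on IMP, so neither can roll over. Completers may also decline. Randomized treatment can influence each of these. Time under observation may then differ between arms, and two arms with the same event rate could show different TEAE percentages.

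**Working it through.** **Inputs from the protocol.** Last dose at Week 50, Day 351 (Section 1.3, footnote k); EOT at Day 365 and EOS at Day 505 (Section 1.3); TE end at last IMP + 154 days (Section 9.2.1); about 70 participants per arm (Section 9.4).

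**Step 1: reproduce the 154 days.** Day 351 + 154 = Day 505 = Week 72. Equivalently, 14 days to EOT plus 140 days (20 weeks) of follow-up is 154. The figure is right for a completer who enters follow-up.

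**Step 2: three kinds of window.**
- Rollover: observed to Day 365 (56 weeks less 4 of screening = 52). Coverage is 365/505 = 72%; 505 − 365 = 140 days (28%) are unobserved, which is 140 of the 154 days after the last dose.
- Completer who does not roll over: observed to Day 505 (72 weeks).
- Early discontinuer: the window ends 154/7 = 22 weeks after the last dose. Last dose at Week 10 gives Week 32; at Week 30, Week 52. With a last dose before Week 30 the window is shorter than a rollover's.

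**Step 3: effect on a crude percentage when the arms do not truly differ.** Assumptions not in the protocol: constant and equal hazard, and rollover shares r of 80% or 90% on itepekimab against 60% on placebo. With p52 the incidence by Week 52, h = −ln(1 − p52)/52 and p72 = 1 − exp(−72h).
- p52 = 70%: p72 = 81.1%.
- p52 = 10%: p72 = 13.6%.

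*Case A: every non-rollover is a completer followed to Week 72.* Arm incidence = r·p52 + (1 − r)·p72.
- 80% v 60%, 70% event: 72.2% v 74.4%, −2.2 points.
- 80% v 60%, 10% event: 10.7% v 11.4%, ratio 0.94.
- 90% v 60%, 70% event: 71.1% v 74.4%, −3.3 points; 10% event, ratio 0.91.

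*Case B: every non-rollover is an early discontinuer, last dose uniform over Weeks 0 to 50.* The window is then uniform over 22 to 72 weeks, and mean incidence is pD = 1 − [exp(−22h) − exp(−72h)]/(50h).
- p52 = 70%: pD = 64.4%; p52 = 10%: pD = 9.0%.
- 80% v 60%, 70% event: 0.8 × 70 + 0.2 × 64.4 = 68.9% v 0.6 × 70 + 0.4 × 64.4 = 67.8%, +1.1 points.
- 80% v 60%, 10% event: 9.8% v 9.6%, ratio 1.02.
- 90% v 60%, 70% event: 69.4% v 67.8%, +1.7 points.

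*Case C: only the extra 20% of placebo non-rollovers are discontinuers; the other non-rollovers in both arms are completers.* 70% event: 72.2% v 0.6 × 70 + 0.2 × 81.1 + 0.2 × 64.4 = 71.1%, +1.1 points.

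The sign depends on why participants do not roll over. If rollover and discontinuation patterns are the same in both arms, the difference is zero in every case.

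**Step 4: scale.** The standard error of a difference for a 70% event with 70 per arm is √(2 × 0.7 × 0.3/70) = 7.7 points. The distortions above are well inside that.

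**The case against.** The strongest reply is that only the parenthesis in Section 9.2.1 is inexact. Section 9 is described as a summary, with technical detail left to the SAP, and truncation at extension entry and exposure-adjusted rates are ordinary SAP content. The effect is also small against sampling error, the rollover shares are assumed, Section 9.4 cites dropout below 5% in the precedent trials, and nothing arises unless LTS18420 opens. The points on size and conditionality stand. The SAP point stands in part: silence on exposure-adjusted rates is not in itself an error. But Section 9.2.1 states a definition that Sections 1.1, 1.3 and 4.4 contradict for rollovers, and Section 9.2.6.1 builds its stated measure on it.

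Three stronger readings are tempting and are not supported.
- *An effective drug would raise rollover and so hide harm.* That needs non-rollovers to have the longer window, as in Case A. If itepekimab participants roll over more because fewer of them discontinue, the extra placebo non-rollovers are discontinuers and the sign reverses (Cases B and C). The protocol gives no basis for assuming that completers differ by arm in willingness.
- *Placebo rollovers' time on open-label itepekimab contaminates the placebo counts.* Section 9.2.1 divides the observation period of this study, which ends at EOT for them, and LTS18420 has its own protocol. No open-label events are planned to enter these tables.
- *Comparing arms on the on-treatment period alone would solve it.* That period does not depend on entry to follow-up, but it ends 14 days after the last dose, so its length still depends on discontinuation.

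**Conclusion.** The point holds as a modest defect in the safety summaries. If LTS18420 opens, the TE window as defined does not match what is observed for rollovers (72% coverage), and the crude TEAE percentages pool windows that depend on post-randomization course. Any bias between arms can go either way and needs rollover or discontinuation to differ by arm. Under assumed rollover gaps of 20 to 30 points and a constant, equal hazard, it is roughly 1 to 3 points for a common event. No direction can be claimed, because the protocol gives no rollover rate and no reasons for declining. The co-primary analyses are untouched. This is a cheap improvement rather than a threat to the trial's conclusions.

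**What to change.** In Section 9.2.1, end the TE period at the earliest of last IMP + 154 days, the first LTS18420 dose (the EOT visit for rollovers) and the end of observation in this study. This wording alone changes no count or percentage; it defines the time at risk.

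In Section 9.2.6.1, report exposure-adjusted incidence rates beside the crude percentages for TEAEs, TESAEs and TEAESIs: participants with at least one event per 100 participant-years of observed TE time, with time counted to first event or end of the window.

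The cost is a wording change and a few extra tables from data already collected. The rates rely on an approximately constant hazard, so they supplement the percentages and do not replace them.

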1.3 SCHEDULE OF ACTIVITIES (SOA)

Procedure	Screening ^a	Intervention Period										EOT/ETD ^b	Follow-up (20 weeks) /EOS ^c	Notes
		0	2	4	6, 8, 10	12	14, 16, 18, 20, 22	24	26, 28, 30, 32, 34	36	38, 40, 42, 44, 46, 48, 50			
Week	-4	0	2	4	6, 8, 10	12	14, 16, 18, 20, 22	24	26, 28, 30, 32, 34	36	38, 40, 42, 44, 46, 48, 50	52	72	
Visit ^d	1 (site)	2 (site)	3 (site)	4 (site)	5-7 (home/call)	8 (site)	9-13 (home/call)	14 (site)	15-19 (home/call)	20 (site)	21-27 (home/call)	28 (site)	29 (site)	
Days ^e	-28	1	15	29	43, 57, 71	85	99, 113, 127, 141, 155	169	183, 197, 211, 225, 239	253	267, 281, 295, 309, 323, 337, 351	365	505	
Informed consent ^f	X													
Inclusion and exclusion criteria	X	X												[Recheck clinical status before randomization and/or first dose of investigational intervention.]
Participant demographics	X													
Medical/surgical history ^g	X													Substances: [drugs, alcohol, tobacco, and caffeine]
AERD screening questionnaire ^h	X													
Record planned endoscopic sinus surgery ⁱ	X	←-----> Every 2 weeks												
Nasal endoscopy ^j	X	X						X				X	X	Central reading

Procedure	Screening ^a	Intervention Period										EOT/ETD ^b	Follow-up (20 weeks) /EOS ^c	Notes
		0	2	4	6, 8, 10	12	14, 16, 18, 20, 22	24	26, 28, 30, 32, 34	36	38, 40, 42, 44, 46, 48, 50			
Week	-4	0	2	4	6, 8, 10	12	14, 16, 18, 20, 22	24	26, 28, 30, 32, 34	36	38, 40, 42, 44, 46, 48, 50	52	72	
Visit ^d	1 (site)	2 (site)	3 (site)	4 (site)	5-7 (home/call)	8 (site)	9-13 (home/call)	14 (site)	15-19 (home/call)	20 (site)	21-27 (home/call)	28 (site)	29 (site)	
Days ^e	-28	1	15	29	43, 57, 71	85	99, 113, 127, 141, 155	169	183, 197, 211, 225, 239	253	267, 281, 295, 309, 323, 337, 351	365	505	
Prior/concomitant/rescue medications	X	-----> Every 2 weeks										X		
Smoking status	X	X	X	X		X		X		X		X	X	Smoking history at Visit 1 and smoking status at all other indicated visits
Study intervention administration														
IRT	X	X	X	X		X		X		X		X		
Randomization		X												
IMP administration ^k		-----> Q2W												
AxMP dispensation		----->												
Efficacy assessments														
CT scan ^l		X						X						
Dispense/collect symptom diary ^m	X												X	

Procedure	Screening ^a	Intervention Period										EOT/ETD ^b	Follow-up (20 weeks) /EOS ^c	Notes
		Week	-4	0	2	4	6, 8, 10	12	14, 16, 18, 20, 22	24	26, 28, 30, 32, 34			

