9.2.6.2 Laboratory variables, vital signs and electrocardiograms

Quantitative analyses

When relevant, for laboratory variables, vital signs and ECG variables, descriptive statistics for results and changes from baseline will be provided for each planned visit, the last value and the worst value (minimum and/or maximum value depending on the parameter) during the on-treatment period. These analyses will be performed using central measurements only (when available) for laboratory variables.

Analyses according to Potentially Clinically Significant Abnormality

PCSA analyses will be performed based on the PCSA list currently in effect at Sanofi at the time of the database lock.

Analyses according to PCSA will be performed based on the worst value during the TE period, using all measurements, either scheduled, nonscheduled or repeated.

For laboratory variables, vital signs and ECG variables, the incidence of participants with at least 1 PCSA during the TE period will be summarized regardless of the baseline level and according to the following baseline status categories:

- Normal/missing.
- Abnormal according to PCSA criterion or criteria.

For ECG, the incidence of participants with at least one abnormal ECG during the TE period will be summarized regardless of the baseline level and according to the following baseline status categories:

- Normal/missing.
- Abnormal.

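### The on-treatment (+14 days) and treatment-emergent (+154 days) periods end on the nominal Week 52 and Week 72 days with no allowance for the permitted windows, so some in-window EOT and EOS safety data fall outside them

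*Protocol*

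**What the plan says.** Protocol section 9.2.1 (General considerations) sets the TE period "from the first IMP administration to the last IMP administration + 154 days (ie, to the end of 20-week safety follow-up period" and, inside it, an on-treatment period "defined as the period from the first IMP administration to the last administration of the IMP + 14 days". What lies between the two limits is the residual treatment period; anything later is post-treatment.

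The Schedule of Activities (section 1.3) fixes the timing. Footnote k: "The last dose will be given 2 weeks prior to the planned EOT visit (Week 50". The Days row for Weeks 38 to 50 reads "267, 281, 295, 309, 323, 337, 351", so Week 50 is Day 351; Week 52 is Day 365 and Week 72 is Day 505. Visits are counted from randomization, not from the last dose: "All subsequent visits will be calculated using this as a reference". The windows are in footnote a ("Window for subsequent visits is +/-3 days") and footnote e ("Window of +/-3 days applies to all visits during IMP administration. Follow up/EOS has a +/-7 day window"). Section 6.1.1 also gives 3 days either way on dosing.

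Section 9.2.6.2 uses the on-treatment period for quantitative laboratory, vital-sign and ECG summaries, including "the last value and the worst value (minimum and/or maximum value depending on the parameter) during the on-treatment period". It uses the TE period for potentially clinically significant abnormalities (PCSA) and for the incidence of abnormal ECGs. Section 9.2.6.1 uses the TE period to classify adverse events.

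**The concern.** Both limits fall exactly on the nominal day of the visit that closes the period, with no margin. A participant who keeps to the schedule can have an EOT or EOS visit after the period has closed, because the visit was a little late, the last dose a little early, or both.

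At EOT the data at risk are the Week 52 laboratory values and vital signs and, above all, the ECG. The Schedule of Activities has an ECG only at screening and at EOT, so an EOT visit 15 days after the last dose leaves that participant with no scheduled on-treatment ECG for the last-value and worst-value summaries.

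At EOS the data at risk are the hematology and chemistry sample, which would leave the PCSA analysis, and adverse events that arise more than 154 days after the last dose but before a late EOS visit. Section 8.4.1 collects adverse events until EOS, but these would be classed as post-treatment. Section 9.2.1 itself says that the TE period reaches the end of the 20-week follow-up; for these participants it does not.

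**Working it through.** **Inputs.** Last dose Week 50, EOT Week 52, EOS Week 72 (section 1.3). Windows: ±3 days on the last dose and EOT, ±7 days on EOS (section 1.3 footnotes a and e; section 6.1.1). Limits: last dose + 14 and + 154 days (section 9.2.1). A visit exactly on the limit is counted as inside.

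**Reproducing the plan's figures.** Day = 7 × week + 1.
- Week 50: 7 × 50 + 1 = 351. Week 52: 365. Week 72: 505.
- 351 + 14 = 365, the nominal EOT day.
- 351 + 154 = 505, the nominal EOS day. Equivalently, 14 + 20 × 7 = 154.

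The plan's equation of + 154 days with the end of follow-up is therefore right on nominal days only.

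**Longest in-window intervals.**
- EOT: (365 + 3) − (351 − 3) = 20 days, 6 beyond the limit.
- EOS: (505 + 7) − (351 − 3) = 164 days, 10 beyond the limit.

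**Share outside the period.** The documents give no distribution of actual dates, so this part rests on assumptions. Let V be the visit's deviation from its nominal day and D that of the last dose. The visit is outside the period when V > D. If both are symmetric about zero and independent, P(V > D) = (1 − P(V = D)) / 2.
- Uniform on whole days, EOT: P(V = D) = 7/49, so P = 21/49 = 42.9%.
- Uniform on whole days, EOS: P(V = D) = 7/105, so P = 49/105 = 46.7%.
- 90% of each date nominal, the rest spread evenly, EOT: P(V = D) = 0.81 + 6 × (0.1/6)² = 0.8117, so P = 9.4%.
- The same for EOS: P(V = D) = 0.81 + 6 × (0.1/14)(0.1/6) = 0.8107, so P = 9.5%.

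| Assumption | EOT > 14 days | EOS > 154 days |
|---|---|---|
| Continuous uniform | about 50% | about 50% |
| Uniform, whole days | 42.9% | 46.7% |
| 50% of dates nominal | 35.4% | 36.6% |
| 70% of dates nominal | 24.8% | 25.2% |
| 90% of dates nominal | 9.4% | 9.5% |

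If dates are uniform but half of the participants have the same deviation at Weeks 50 and 52, the EOT share is 0.5 × 42.9% = 21.4%.

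**Effect of widening the limits** (uniform, whole days).
- Adding the visit window only (+ 17 and + 161 days) leaves 6/49 = 12.2% of EOT and 6/105 = 5.7% of EOS visits outside.
- Adding the visit and dosing windows (+ 20 and + 164 days) leaves none.

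**The case against.** The definitions are coherent as exposure windows: 14 days is one dosing interval, and 154 is that interval plus 20 weeks. The rule is the same in every blinded arm, and nothing shows a bias between arms. Section 9 calls itself a summary, and a SAP may assign in-window assessments to visits. This supports treating the point as modest, but it does not remove it: the limits are fixed in the protocol, and a SAP that changed them would contradict it.

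The objection also narrows the consequences, and these limits stand:
- A late EOT value is still far inside the TE period, so it counts for PCSA and abnormal-ECG incidence. A reader might infer that it is lost from the treatment-emergent tables; section 9.2.6.2 does not support that. It leaves the last-value and worst-value summaries, and the by-visit row for Week 52 may be read as keeping it.
- Laboratory values (Weeks 12, 24, 36) and vital signs (Weeks 2 to 36) have earlier on-treatment measurements. Only the ECG has none.
- Adverse events are classified by when they developed, worsened or became serious. An earlier event reported at a late EOS visit is still treatment-emergent, and post-treatment events are an analysed category.
- Participants entering LTS18420 have no EOS visit, and no ECG or vital signs are scheduled at EOS.

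A reader might also count a missed Week 50 dose, or an early-discontinuation visit on the day the skipped dose was due, as instances of the same fault. Neither is. In the first case EOT is nominally 28 days, two dosing intervals, after the last dose, and an exposure-based rule works as intended in calling that off treatment. In the second the visit is nominally on day 14 and so inside the period.

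**Conclusion.** The point holds in a limited form. Followed as written, section 9.2.1 puts some protocol-compliant EOT visits (15 to 20 days after the last dose) outside the on-treatment period and, for participants not entering LTS18420, some compliant EOS visits (155 to 164 days) outside the TE period. The day arithmetic needs no assumption beyond a Week 50 dose given within its window.

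The frequency does need one. It is tempting to say that over 40% of visits are affected, but the documents do not support that as a flat statement: it requires dates spread widely and independently across the windows. About 43% (EOT) and 47% (EOS) apply under independent whole-day uniform dates, and about 9% if 90% of dates are nominal. Similar deviations at Weeks 50 and 52 would lower the EOT figure further.

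The main losses are the sole scheduled post-baseline ECG from the on-treatment last-value and worst-value summaries, and late EOS hematology and chemistry from the PCSA analysis. No primary or key secondary efficacy analysis is touched. This is a cheap improvement to the safety definitions.

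**What to change.** In section 9.2.1, and in the SAP to match:
- End the on-treatment period at last dose + 20 days (14 + 3 + 3).
- End the TE period at the later of last dose + 154 days and the in-window EOS visit, at most last dose + 164 days (154 + 7 + 3).
- For participants who roll over, end it at the first LTS18420 dose. The on-treatment period lies within the TE period, so it stops there too.
- Reword the explanation in parentheses so that it is true for EOS visits on any day of their window.

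The cost is one paragraph in the protocol and its counterpart in the SAP, best settled before database lock. The downside is that a few more days of events and measurements count as on-treatment or treatment-emergent, which is the cautious direction for safety reporting.
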